#### **6.5 Prior and Concomitant Medications**

All prior and concomitant therapies will be coded using the latest WHO-DRUG version, and classified using Anatomical therapeutic chemical classification system (ATC level 4 class).

Medications will be classified as prior or concomitant, as reported in the CRF. Prior medications are medications which ended before the signing of informed consent. Concomitant medications are medications which are ongoing at signing of informed consent or which started after the signing of informed consent.

Prior and concomitant therapies will be tabulated by ATC level 4 class and generic term using the safety population. Multiple records of the same generic term for the same subject and ATC level 4 class will be counted only once. The table will therefore present subjects, not occurrences. The tables will be sorted by decreasing frequency (overall). Additionally, all information will be listed.

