#### 14.2.6 Duration of supplemental oxygen therapy

This is based on concomitant medication records.

For Baseline assessment a subject is considered being on oxygen supplementation at baseline if oxygen was received between hospital admission and the first dose of study medication. For this derivation, both prior and concomitant medications are considered

Total duration will be calculated as the total number of hours (taking into account the sum of the actual time windows the concomitant medication was received) using concomitant treatment coded as "Oxygen" from admission until trial termination and from first dose until trial termination. Missing information on concomitant medication records will be imputed in the following way

- If start time is missing: impute with 0:00 .

- If end time is missing: impute with 23:59.
- If start day/month is missing: impute with first day (01) / month (Jan) if this falls within trial window, otherwise impute with day/month of first contact in the trial.
- If end day/month is missing: impute with last day (31) / month (Dec) if this falls within trial window, otherwise impute with day/month of trial termination.

In case of overlapping records, the duration will be calculated only once for the overlapping part of the records.

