#### 14.2.7 Duration of feeding support

This is based on concomitant medication records.

For Baseline assessment a subject is considered being on feeding support at baseline if support was received between hospital admission and the first dose of study medication. For this derivation, both prior and concomitant medications are considered

Following coded terms will be considered for feeding support provided the route of administration is intravenous or nasogastric.

AMINO ACIDS NOS  
AMINOVEN  
CALCIUM GLUCONATE  
DEXTROSE AND SODIUM CHLORIDE INJECTION  
DEXTROSE IN LACTATED RINGER'S  
ELECTROLYTES NOS  
ELECTROLYTES NOS W/GLUCOSE  
GLUC5% W/RINGER BAXTER  
GLUCOSE  
GLUKOSALINA /06282701/  
INFANT FORMULAS  
ISOLYTE /06504901/  
ISOLYTE P DEXTROSA  
JONOSTERIL /01263001/  
MAGNESIUM SULFATE  
MATERNA /02266601/  
OSMOTAN  
POTASSIUM CHLORIDE  
PROTEIN HYDROLYSATE  
RICE /08368701/  
RINDEX /07339201/  
RINGER-LACTATE

SODIUM CHLORIDE  
SODIUM GLYCEROPHOSPHATE

Total duration will be calculated as the total number of hours (taking into account the sum of the actual time windows the concomitant medication was received) using concomitant treatment from the above list from admission until trial termination and from first dose until trial termination. Missing information on concomitant medication records will be imputed in the following way

- If start time is missing: impute with 0:00 .
- If end time is missing: impute with 23:59.
- If start day/month is missing: impute with first day (01) / month (Jan) if this falls within trial window, otherwise impute with day/month of first contact in the trial.
- If end day/month is missing: impute with last day (31) / month (Dec) if this falls within trial window, otherwise impute with day/month of trial termination.

In case of overlapping records, the duration will be calculated only once for the overlapping part of the records.

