**Table 14.2.6.4: Hospitalisation – Total time of reported oxygen supply.**

Descriptive statistics of total time of oxygen supply. Both time from admission to EOS as time from first dose to EOS will be reported

Population: mITT population.

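### As written, the oxygen and feeding-support totals counted from admission leave out support records that ended before consent

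*SAP*

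**What the plan says.** SAP 6.5 splits medications at consent. On one side, "Prior medications are medications which ended before the signing of informed consent". On the other, "Concomitant medications are medications which are ongoing at signing of informed consent or which started after the signing of informed consent". The two classes do not overlap.

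SAP 14.2.6 (oxygen) and 14.2.7 (feeding support) each contain two derivations:

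- **Baseline flag.** An infant is on support at baseline if it was received between hospital admission and first dose. The record source is spelled out: "For this derivation, both prior and concomitant medications are considered".
- **Total duration.** Hours are summed from concomitant treatment over two windows. For oxygen these are "from admission until trial termination and from first dose until trial termination". For feeding support the wording is "using concomitant treatment from the above list from admission until trial termination and from first dose until trial termination". Overlapping records are counted once.

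The description of Table 14.2.6.4 says "Both time from admission to EOS as time from first dose to EOS will be reported", and Table 14.2.6.5 does the same for feeding support. Tables 14.2.6.6 and 14.2.6.7 cross-tabulate the baseline flag against post-baseline use. SAP 4.3.3 lists both durations among the other endpoints, and SAP 7.3 plans no test for them.

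**The concern.** The from-admission total differs from the from-first-dose total only by the hours before the first dose, so covering those hours is its sole purpose. That is where the rule drops records. A figure labelled as running from admission could be too short. It could also disagree with the baseline flag for the same infant, who is counted as on oxygen at baseline while those hours are absent from the duration table.

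The result would also depend on when consent was signed and on whether the site closed one record and opened another when the device, flow or fluid changed. Neither describes how long the infant needed support.

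**Working it through.** The documents give no value for these durations, so there is no figure to reproduce. The check applies the rule as written.

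**1. Can support precede consent?** Yes. Screening starts at consent, and randomisation may come up to 24 hours after arrival (Protocol 3.4.1.1). Inclusion criterion 7 can be met through oxygen supplementation with a documented value before it, or through feeding support, so support in the early hospital hours is plausible.

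**2. What is lost?** For one infant:

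Loss = (hours covered by prior and concomitant records since admission) − (hours covered by concomitant records since admission)

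This equals the hours in records that ended between admission and consent and are not overlapped by a concomitant record. Consent precedes randomisation, so the loss is under 24 h if the 24-hour rule is met and admission is no earlier than arrival.

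**3. Hypothetical infants.** All hours are assumptions, counted from admission.

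*Consent at 12 h, first dose at 15 h:*

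| Infant | Oxygen records | Concomitant only | Prior and concomitant | From first dose, either rule |
|---|---|---|---|---|
| A | 1–9 h, then 14–60 h | 60 − 14 = 46 h | 8 + 46 = 54 h | 60 − 15 = 45 h |
| B | 1–60 h, one record | 60 − 1 = 59 h | 59 h | 45 h |

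Infant A loses 8 h, or 8/54 = 14.8%. Infant B loses nothing, because a record running through consent is concomitant and counts from its actual start.

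*Consent at 8 h, effect of record-keeping alone:* mask oxygen from 0.5 to 6 h and cannula from 6 to 48 h, entered as two records, gives 48 − 6 = 42 h. The hours received are 5.5 + 42 = 47.5 h, so 5.5/47.5 = 11.6% is lost. The same course entered as one record from 0.5 to 48 h gives 47.5 h and no loss.

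*Limiting case:* an infant whose only oxygen ended before consent is flagged as on oxygen at baseline and has a total of 0 h.

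**4. Effect on a group mean.** Understatement = (share of infants with a closed pre-consent record) × (mean hours lost in those infants). The documents give neither input. Over an assumed range:

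- 5% × 2 h = 0.1 h
- 10% × 6 h = 0.6 h
- 25% × 6 h = 1.5 h
- 25% × 12 h = 3.0 h
- 50% × 24 h = 12 h, as an extreme

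The from-first-dose mean does not change in any of these.

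**The case against.** The best counter-argument is that both sections open by saying they rest on concomitant medication records, and that line also covers the baseline flag, which expressly uses prior entries. The phrase could therefore mean the whole medication dataset. SAP 7.3 describes the oxygen duration as all reported supply time and excludes nothing. On that reading no hours are lost. The reading is possible, but it would make the sentence that brings in prior records for the flag redundant. That sentence is tied to the flag alone, and the next derivation reverts to concomitant treatment. At best the text is ambiguous, and two programmers could produce different tables.

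The eligibility rules also narrow the problem. At screening and at randomisation, symptoms must not be improving and two of three severity criteria must hold (Protocol 3.2.1). The 0 h case is therefore less likely, though still possible.

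A reader might infer three stronger things that the documents do not support:

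- *That early closed records are typical.* Protocol 3.3.8 lists what is recorded for each medication but gives no rule for closing a record when the device or fluid changes, and no frequency is stated.
- *That treatment comparisons are biased.* The lost hours precede randomisation, so no systematic difference between arms is expected.
- *That a programming change alone restores the missing hours.* Protocol 3.3.8 requires only previous medications relevant to eligibility. Much oxygen and feeding support may qualify under criterion 7, but complete capture since admission is not promised.

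**Conclusion.** The rule as written omits support that ended between admission and consent, and nothing elsewhere in the SAP restores it. The from-admission totals can therefore be shorter than their label says and can disagree with the baseline flag.

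This is a minor defect. The loss is zero for an infant whose support runs through consent in one record, and under 24 h otherwise, provided the 24-hour randomisation rule is met and admission is no earlier than arrival. The effect on a group mean cannot be fixed from the documents; the range shown rests on assumed shares and hours. The totals from first dose, the primary analysis and the Global Severity Score comparison are untouched.

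**What to change.** In SAP 14.2.6 and 14.2.7, state that the from-admission total uses prior and concomitant records, cut at the admission date and time, as the baseline flag already does in substance. Leave the from-first-dose total unchanged.

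Before relying on it, confirm that the eCRF captures all oxygen and feeding support since admission, including support that ended before consent. If it does not, keep the present rule and label the from-admission column in Tables 14.2.6.4 and 14.2.6.5 as covering concomitant records only.

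The cost is a few words in two SAP sections, one filter in the derivation, and one check of the eCRF.

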#### 14.2.7 Duration of feeding support

This is based on concomitant medication records.

For Baseline assessment a subject is considered being on feeding support at baseline if support was received between hospital admission and the first dose of study medication. For this derivation, both prior and concomitant medications are considered

Following coded terms will be considered for feeding support provided the route of administration is intravenous or nasogastric.

AMINO ACIDS NOS  
AMINOVEN  
CALCIUM GLUCONATE  
DEXTROSE AND SODIUM CHLORIDE INJECTION  
DEXTROSE IN LACTATED RINGER'S  
ELECTROLYTES NOS  
ELECTROLYTES NOS W/GLUCOSE  
GLUC5% W/RINGER BAXTER  
GLUCOSE  
GLUKOSALINA /06282701/  
INFANT FORMULAS  
ISOLYTE /06504901/  
ISOLYTE P DEXTROSA  
JONOSTERIL /01263001/  
MAGNESIUM SULFATE  
MATERNA /02266601/  
OSMOTAN  
POTASSIUM CHLORIDE  
PROTEIN HYDROLYSATE  
RICE /08368701/  
RINDEX /07339201/  
RINGER-LACTATE

SODIUM CHLORIDE  
SODIUM GLYCEROPHOSPHATE

Total duration will be calculated as the total number of hours (taking into account the sum of the actual time windows the concomitant medication was received) using concomitant treatment from the above list from admission until trial termination and from first dose until trial termination. Missing information on concomitant medication records will be imputed in the following way

- If start time is missing: impute with 0:00 .
- If end time is missing: impute with 23:59.
- If start day/month is missing: impute with first day (01) / month (Jan) if this falls within trial window, otherwise impute with day/month of first contact in the trial.
- If end day/month is missing: impute with last day (31) / month (Dec) if this falls within trial window, otherwise impute with day/month of trial termination.

In case of overlapping records, the duration will be calculated only once for the overlapping part of the records.

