- e. For subjects who discontinue the study before Day 28, the Withdrawal visit will be conducted on the day of withdrawal as long as there has been no withdrawal of consent. If the Withdrawal visit assessments are performed within 6 hours after the Day 1, Day 2, Day 3, or in-hospital post-treatment Day assessments have been performed, the assessments already done at the prior time point do not need to be repeated and only the additional assessments to be performed on the Withdrawal Visit will need to be performed. No EOS visit needs to be performed after the Withdrawal Visit. In case subjects are hospitalized beyond the Day 14 FU visit, the additional assessments (in addition to the in-hospital post treatment period assessments) of the Day 14 FU visit need to be done on Day 14.
- f. RSV infection will be confirmed either according to routine site practice (PCR or diagnostic quick test), or using a (Sponsor-provided) commercial kit.
- g. Hospitalization information will include occurrence of ICU transfer, apnea episodes, initiation and type of ventilation and hospital/ICU discharge information. Assessment of Clinical Response will be done with collection of date and time of adequate oral feeding to enable discharge as well as adequate stable oxygen saturation on room air of  $>92\%$  over a period of at least 4 hours.
- h. Study drug will be administered via nebulization using the study-specific device. One dose consists of 2 serial nebulizations.
- i. A mid-turbinal nasal swab should be taken using provided kits and following specific instructions in case the subject is re-hospitalized or consults the Investigator for a respiratory condition after hospital discharge.
- j. A nasal swab should only be collected during the in-hospital post-treatment period on the day of hospital discharge.
- k. Physical examination includes examination of abdomen and skin and ears/nose/throat. Lung auscultation is listed separately as it is to be assessed more frequently.
- l. Continuous monitoring of SpO2 needs to be done until the clinical response criterion for oxygen has been met and/or in case saturation monitoring is to be continued according to the Investigator's judgment.
- m. Type of feeding support, if any, and feasibility of oral feeding.
- n. To assess wheezing, crackles/crepitation and other abnormalities in lung auscultation.

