### 3.2.1. INCLUSION CRITERIA

A subject will be eligible for study participation if he/she meets all of the following criteria at screening and randomization, unless specified otherwise:

1. Subject is a male or female infant or young child aged 28 days to <2 years with gestational age  $\geq$  33 weeks at screening.
2. Subject weighs between  $\geq$  3.0 kg and < 15.0 kg at screening.
3. Subject is otherwise healthy, but is hospitalized for and clinically diagnosed with RSV LRTI (bronchiolitis or broncho-pneumonia), i.e., showing typical clinical signs and symptoms such as tachypnea, wheezing, cough, crackles, use of accessory muscles and/or nasal flaring.
4. Subject has a positive RSV diagnostic test at screening.##
5. Subject is expected to have to stay in the hospital for at least 24 hours (according to the Investigator's judgment at screening).
6. Symptoms likely related to RSV infection (i.e., the symptoms present need to be probably linked to the current RSV infection according to Investigator's judgment) have appeared within 4 days of screening and are not yet improving at screening and randomization.
7. Subject fulfils at least two of the following RSV disease severity criteria at screening and randomization:
  - Inadequate oral feeding that requires feeding support (i.e., nasogastric tube or i.v. line)
  - Inadequate oxygen saturation defined as:
    - Oxygen saturation ( $SpO_2$ )  $\leq$  92% on room air or
    - Requiring oxygen supplementation to maintain oxygen saturation  $>$  90% with documented pre-supplementation value  $\leq$  92%
  - Signs of respiratory distress defined as:
    - Respiratory rate  $\geq$  50 per minute in infants up to 12 months of age, and  $\geq$  40 per minute in children above 12 months and/ or
    - Moderate or marked respiratory muscle retractions

---

## RSV infection will be confirmed either according to routine site practice (PCR or diagnostic quick test), or using a (Sponsor-provided) commercial kit.

8. Subject has normal psychomotor development.
9. Parent(s)/legal guardian(s) provide written informed consent in accordance with locally approved consent process at screening.
10. The parent(s)/legal guardian(s) are able and willing to comply with the study protocol procedures.

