### **3.3.8. CONCOMITANT THERAPY**

Any concomitant medication (including over-the-counter medications and herbal supplements) taken during the study (i.e., from signing of ICF until the subject's last visit), must be recorded in the eCRF. Items to be recorded concerning concomitant medication include: dose and units of dose, start and end date, administration frequency, route of administration, therapeutic indication, brand name (or generic name if brand name is not available). Of note, previous medications relevant for eligibility will also be recorded in the eCRF.

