- Duration of severe disease (in hours) defined as the time between hospital admission and achieving clinical response will be summarized using KM estimates. The time to event for subjects with missing data and/or who did not reach the clinical response during the trial will be censored at the last nonmissing assessment of blood oxygen level in the vital signs domain (VSTESTCD=OXYSAT) or assessment of adequate oral feeding (DCTESTCD=FEDADQ).
- A cross-tabulation will present the proportion of subjects on oxygen supplementation at baseline versus post-baseline (i.e., any time between first dose date/time and end of study) per treatment group. Additionally, duration of supplemental oxygen therapy (in hours) defined as total time of reported oxygen supply will be calculated based on concomitant medication (CM) records with coded term 'Oxygen' and summarized descriptively. In case of missing CM information a worst case imputation will be applied (see section 14.2.6 for calculation and imputation rules).
- A cross-tabulation will present the proportion of subjects on feeding support at baseline versus post-baseline (i.e., any time between first dose date/time and end of study) per treatment group. Additionally, duration of feeding support (in hours) defined as total time of reported feeding support will be calculated based on concomitant medication records. In case of missing CM information a worst case imputation will be applied (see section 14.2.7 for calculation and imputation rules).
- Incidence of initiation of invasive and non-invasive ventilation (continuous positive airway pressure, bilevel positive airway pressure and high flow ventilation) as well as incidence of apnea will be tabulated. Additionally, duration of invasive and non-invasive ventilation will be summarized descriptively (in hours - see Section 14.2.8 for calculation method).
- The number and percentage of subjects transferred to ICU and duration of ICU stay (in days – see section 14.2.9 for calculation method) will be summarized using descriptive statistics
- Parent(s)/Caregiver(s) diary assessment will be reported as
  - Frequency tabulation over time (condition as before RSV, severity of cough, severity trouble breathing and severity wheezing).

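### Feeding support is derived from medication terms and route alone, so its status and duration can be misclassified in both directions

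*SAP*

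**What the plan says.** SAP 7.3 introduces the endpoint: "duration of feeding support (in hours) defined as total time of reported feeding support will be calculated based on concomitant medication records". SAP 14.2.7 repeats the source ("This is based on concomitant medication records") and gives the selection rule: "Following coded terms will be considered for feeding support provided the route of administration is intravenous or nasogastric". The list has 24 coded terms. It includes glucose and Ringer solutions, amino acids, protein hydrolysate and infant formulas, and also "MAGNESIUM SULFATE", "ELECTROLYTES NOS", calcium gluconate, potassium chloride and sodium chloride as terms of their own. No term names breast or human milk.

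Hours are summed from admission and from first dose to trial termination. A missing start time becomes 0:00 and a missing end time 23:59. Overlapping records are counted once. The same records decide who is on feeding support before and after first dose in the cross-tabulation.

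The protocol holds two further pieces of information that this derivation does not use:

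- Section 3.3.8 requires each medication to be recorded with, among other items, "administration frequency, route of administration, therapeutic indication, brand name".
- Footnote m to the Schedule of Assessments defines the feeding assessment as "Type of feeding support, if any, and feasibility of oral feeding".

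Inclusion criterion 7 shows what the protocol means by the term: "Inadequate oral feeding that requires feeding support (i.e., nasogastric tube or i.v. line".

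**The concern.** A term plus a route does not say why a product was given. I.v. saline for hydration and i.v. saline for some other purpose carry the same term and route, so the rule cannot tell them apart. In the other direction, a milk feed reaches the endpoint only if it was entered as a medication and coded to a listed term. Protocol 3.3.8 asks for medications, and nothing there tells sites to enter milk feeds. Breastfeeding is common enough in this population to be collected as a baseline characteristic.

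At stake is whether the duration of feeding support and the baseline versus post-baseline table describe what they are labelled as describing, and whether they agree with the other feeding results in the same report. The trial is also meant to help choose endpoints for later development (Protocol 3.1.2), so a noisy derivation could mislead that choice.

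**Working it through.** The plan states no figure for this endpoint, so there is none to reproduce. The check applies the rule as written.

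**Inputs.** From SAP 14.2.7: the 24-term list, the route condition, the imputed times 0:00 and 23:59, and the overlap rule. From Protocol 3.2.1: feeding support means a nasogastric tube or an i.v. line. From Protocol 3.3.8: indication is collected. From the Schedule of Assessments: type of feeding support is collected at screening, at pre-dose and 5 h on Days 1 and 2, at pre-dose and 2 h on Day 3, and morning and evening in the in-hospital post-treatment period.

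**Step 1: what decides inclusion.** A record counts if its term is on the list and its route is i.v. or nasogastric. Indication does not enter, so two records that differ only in indication get the same result.

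**Step 2: hours wrongly counted.** Take one i.v. record of a listed term, given for a purpose other than feeding or hydration, on one known date without clock times.

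- No other listed record that day: 23:59 − 0:00 = 23 + 59/60 = 23.98 h.
- Wholly inside another listed record: 0 h added, because overlap counts once.

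A false single-day record therefore adds between 0 and 23.98 h.

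**Step 3: hours missed.** Assume an infant fed breast milk by nasogastric tube for 48 h, with no record under a listed term. The counted duration is 0 h, a shortfall of 48 − 0 = 48 h. The 48 h is an assumption; the counted value is 0 h whatever the true duration. In Table 14.2.6.7 this infant is not on support, although criterion 7 names a nasogastric tube as feeding support.

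**Step 4: agreement with other outputs.** Table 14.2.4.5 tabulates feeding support at each timepoint as part of the evolution of clinical symptoms. The Global Severity Score (GSS) gives 3 feeding points to an infant on feeding support (SAP 14.2.2). The infant in Step 3 can be on support in both and not on support in Table 14.2.6.7. Nothing in the SAP reconciles them.

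**Step 5: can the net bias be sized?** For an arm of n infants, the shift in mean duration is (F − M)/n, where F is total hours wrongly counted and M total hours missed. The planned n is 45. The documents give neither F nor M, so neither the size nor the sign of the shift can be stated.

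**The case against.** The strongest reply is that i.v. fluids belong in this endpoint, and that stands. Criterion 7 names the i.v. line alongside the tube, standard of care treats fluid and food supplementation as one item (Protocol 3.3.8), and adequate oral feeding is judged by hydration (Protocol 3.4.4.1). Saline, glucose, Ringer or electrolytes given to an infant who cannot feed are correctly counted. A reader might infer from the list that the endpoint measures the wrong treatment; the documents do not support that. Magnesium sulfate and calcium gluconate are listed with amino acids and sodium glycerophosphate, so they may be additives to i.v. nutrition, and they add no time when they overlap another listed record.

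A reader might also construct a large effect. A seven-day i.v. diluent record entered by date only would give 7 × 24 h less one minute, about 168 h, and 168/45 = 3.7 h on an arm mean. This is arithmetic on a hypothetical. Nothing says that sites enter diluents as separate records, and the example also needs seven continuous days, no clock times and no overlap with genuine support.

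The breast-milk gap depends on how sites record and code nasogastric milk, which the documents do not state. Listed terms such as MATERNA, RICE and protein hydrolysate may also be feeds, so infant formulas cannot be called the only milk-type term. What remains is that no term names breast milk.

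The direct feeding record is already reported elsewhere (Table 14.2.4.5, and time to adequate oral feeding in Table 14.2.2.1), so a reader can cross-check. Medication records are also a defensible source of hours: the feeding assessment starts at screening, so it cannot time support between admission and screening, and it is not done at 2 h on Days 1 and 2. That argues against replacing the source. It does not argue against filtering and reconciling it.

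**Conclusion.** The point holds as a misclassification risk in both directions. Without an indication filter, i.v. products given for other purposes can count, at up to 23.98 h for a single-day record without clock times that overlaps no other listed record. Without a breast-milk term or any use of the recorded type of support, an infant on nasogastric breast milk with no listed record scores 0 h and is classed as unsupported. Both results follow from the rule as written; how often they arise is unknown.

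The reach is limited. This is an 'other' endpoint added in the SAP (sections 4.3.3 and 13), summarised descriptively with no planned test, and neither of its tables is flagged for topline results. The primary endpoint is untouched. The GSS feeding item appears to come from the visit assessment: SAP 14.2.2 applies its interval rule for recorded episodes to apnea, hospital stay, oxygen and ventilation, not to feeding support. The rule is the same in all arms, and the documents give no basis for claiming bias in favour of any one of them. This is a cheap improvement worth making.

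**What to change.** Amend SAP 14.2.7 as follows:

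1. Keep medication records as the timing source, but include only those whose recorded indication is feeding, nutrition or hydration.
2. Reconcile them with the eCRF type of feeding support. A subject recorded at a visit as on nasogastric or i.v. support counts as on support, including one fed breast milk by tube. Where no timed record exists, bound the duration by the assessment timepoints.
3. Use this one derivation for the duration table (14.2.6.5) and the cross-tabulation (14.2.6.7).

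The cost is SAP wording and the reprogramming of one derivation from data already collected. The drawback is precision: some durations will be known only to the nearest assessment. Overnight during treatment, the nominal gap from the 5 h assessment to the next pre-dose assessment is about 24 − 5 − 2 = 17 h to 24 − 5 = 19 h, ignoring the visit windows and nebulization time. Support before screening still rests on medication records.
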